9.3 Statistical analyses

9.3.1 General considerations

Descriptive statistics will be performed as described in the sections [9.3.2](#) and [9.3.3](#).

9.3.2 Primary endpoint/estimand analysis

The primary endpoint number of adverse events will be used to support the primary objective of evaluating safety of once-weekly somapacitan during 26 weeks of treatment in children with SGA, TS, NS or ISS based on the primary estimand corresponding to the on-treatment data points set.

To support the primary estimand descriptive statistics (Number and percentage of participants who experienced adverse events, the number of events) will be derived in addition to the event rate per 100 patient years of exposure. The primary endpoint will be summarised for each indication, SGA, TS, NS or ISS. All adverse events with onset after the first administration of trial product and up until end of treatment or 14 days after last trial product administration, whichever comes first, will be included in the analysis. The adverse events will be summarised by MedDRA (Medical Dictionary for Regulatory Activities) system organ class and MedDRA preferred term. Adverse events with onset 14 days or more after last trial product administration will be reported in a separate listing.

9.3.3 Secondary endpoints/estimands analysis

Supportive Secondary Safety endpoints/estimands

The supportive secondary safety estimand regarding the incidence of AEs possibly or probably related to somapacitan from baseline up to week 26 of somapacitan treatment will be evaluated in a similar way as the primary endpoint including AEs possibly or probably related to somapacitan in the endpoint attribute.

The supportive secondary safety estimand regarding the incidence of AEs from baseline up to week 156 of somapacitan treatment will be evaluated in a similar way as the primary endpoint substituting 156 weeks for 26 weeks.

Supportive Secondary efficacy endpoints/estimands

Table 9-1 Overview of supportive secondary Efficacy endpoints

Title	Time frame	Unit	Details
Height velocity	From baseline (week 0) to visit 7 (week 26).	cm/year	Derived as HV at week 26 = (height at 26 weeks visit – height at baseline)/(time from baseline to 26 weeks visit in years).

Title	Time frame	Unit	Details
Change in Height SDS	From baseline (week 0) to visit 7 (week 26).	Score ^a	
Derived as the Height SDS value at baseline week 0 subtracted from the Height SDS value at week 26 (visit 7).
 
Height SDS is derived as:
 $\text{Height SDS}_i = \frac{\left(\frac{\text{Height}_i}{\text{population median}} \right)^{\text{Skewness}} - 1}{\text{Skewness} * \text{population SD}}$ 
where i indicates the visit. The population median and standard deviation are the ones corresponding to the age at visit i. The population median and standard deviation and skewness are based on reference data.²

Change in Height Velocity SDS	From baseline (week 0) to visit 7 (week 26).	Score ^a	
Derived as the Height Velocity SDS value at baseline week 0 subtracted from the Height Velocity SDS value at week 26 (visit 7). Height Velocity SDS is derived as:
 $\text{HV SDS}_i = \frac{\text{HV}_i - \text{population mean HV}}{\text{population SD}}$ 
where i indicates the visit. The population mean and standard deviation corresponding to the age at visit i. The population mean and standard deviation are based on reference data.^{2,53}

Change in IGF-I SDS	From baseline (week 0) to visit 7 (week 26).	Score ^a	
Derived as the IGF-I SDS value at baseline week 0 subtracted from the IGF-I SDS value at week 26 (visit 7).
 
IGF-I SDS is derived as:
 $\text{IGF-I SDS}_i = \frac{\left(\frac{\text{IGF-I}_i}{\text{population median}} \right)^{\text{Skewness}} - 1}{\text{Skewness} * \text{population SD}}$ 
where i indicates the visit. The population median and standard deviation are the ones corresponding to the age at visit i. The population median and standard deviation and skewness are based on reference data.⁵⁴

Change in IGFBP-3 SDS reported for each indication separately.	From baseline (week 0) to visit 7 (week 26).	Score ^a	
Derived as the IGFBP-3 SDS value at baseline week 0 subtracted from IGFBP-3 SDS value at week 26 (visit 7).
 
IGFBP-3 SDS is derived as:

Title	Time frame	Unit	Details
			$IGFBP-3\ SDS_i = \frac{\left(\frac{IGFBP-3_i}{\text{population median}} \right)^{\text{Skewness}} - 1}{\text{Skewness} * \text{population SD}}$ 
where i indicates the visit. The population median and standard deviation are the ones corresponding to the age at visit i. The population median and standard deviation and skewness are based on reference data.⁵⁵

^aPositive score indicates that the value is closer to or above the reference population compared to baseline.

Height velocity, Change in Height SDS and Change in Height Velocity SDS

The clinical question of interest for the supportive secondary efficacy endpoints Height velocity, Change in Height SDS and Change in Height Velocity SDS are: What is the mean Height velocity, Change in Height SDS or Change in Height Velocity SDS after 26 weeks of somapacitan treatment for each group of previously treated (yes/no) in the four populations (SGA, TS, NS or ISS) regardless of dose reduction due to IGF-I or AE, regardless of treatment discontinuation for any reason and regardless of initiation of ancillary therapy or medication with a special focus?

The supportive secondary estimands are defined for each of the four populations (SGA, TS, NS or ISS) with five attributes:

- The treatment condition of interest is defined as somapacitan treatment with or without ancillary therapy or medication with a special focus (treatment policy strategy).
- The population targeted by the clinical question: The treatment effect will be assessed separately for each group of previously treated (yes/no) in the four populations (SGA, TS, NS or ISS).
- Endpoints:
 - Height velocity from baseline (week 0) to visit 7 (week 26)
 - Change in Height SDS from baseline (week 0) to visit 7 (week 26)
 - Change in Height Velocity SDS from baseline (week 0) to visit 7 (week 26)

Remaining intercurrent events: The 4 intercurrent events ‘dose reduction due to IGF-I or AE’, ‘treatment discontinuation for any reason’, ‘initiation of ancillary therapy’ and ‘medication with a special focus’, are all addressed by the treatment condition of interest attribute. There are no remaining intercurrent events.

- Population-level summary: Mean change

Rationale for estimands: The estimands assess the expected benefit a future population (SGA, TS, NS or ISS) can achieve if prescribed somapacitan. By not placing any restrictions on treatment adherence, these estimands aim to obtain a difference as close as possible to the one that can be

expected in clinical practice, provided that the dose reduction, treatment adherence and use of ancillary therapy in the study reflects what would be seen in clinical practice.

The supportive secondary estimands will be evaluated based on all participants where both baseline and week 26 data are collected. To support the supportive secondary estimands SD, median, min and max values will also be derived for the supportive secondary endpoints.

Change in IGF-I SDS and Change in IGFBP-3 SDS

The clinical question of interest for the supportive secondary efficacy endpoints Change in IGF-I SDS and Change in IGFBP-3 SDS from baseline (week 0) to visit 7 (week 26) are: What is the mean change after 26 weeks of somapacitan treatment within each group of previously treated (yes/no) in the four populations (SGA, TS, NS or ISS) patients while on treatment regardless of dose reduction due to IGF-I or AE or medication with a special focus?

The supportive secondary estimands are defined for each of the four populations (SGA, TS, NS or ISS) with five attributes:

- The treatment condition of interest is defined as somapacitan regardless of dose reduction or medication with a special focus.
- The population targeted by the clinical question: The treatment effect will be assessed separately for each group of previously treated (yes/no) in the four populations (SGA, TS, NS or ISS)
- Endpoints:
 - Change in IGF-I SDS from baseline week 0 to week 26
 - Change in IGFBP-3 SDS from baseline week 0 to week 26
- Remaining intercurrent events:
 - Treatment discontinuation for any reason: Participant's data will be included up to 14 days after treatment discontinuation. Data collected 14 days after the intercurrent event will be regarded as not relevant for the estimation of the treatment effect.
 - Initiation of medication with a special focus: Addressed by the treatment condition of interest attribute.
 - Dose reduction due to IGF-I or AE: Addressed by the treatment condition of interest attribute. There are no remaining intercurrent events.
- Population-level summary: Mean change

Rationale for estimand: The supportive secondary estimand assesses the expected benefit a future population (SGA, TS, NS or ISS) can achieve if prescribed somapacitan if no treatment discontinuation had occurred.

The supportive secondary estimands will be evaluated based on all participants where both baseline and week 26 data are collected. To support the supportive secondary estimands SD, median, min and max values will also be derived for the supportive secondary endpoints.

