The rationale for amending the protocol is to offer participants that complete the current 3 year study period before somapacitan is available for prescription for children with SGA, TS, NS or ISS in their country to continue in the study in an additional extension period II, during which they will receive treatment with somapacitan until somapacitan is available for prescription in their country or October 2027 at the latest. This will allow for collection of additional clinical data on long-term exposure of somapacitan for safety and clinical efficacy.

Section # and name	Description of change	Brief rationale
Section 1.1 Synopsis Section 4.1 Overall design	Extension period II was added to offer participants that complete the current 3 year study period before somapacitan is available for prescription for children with SGA, TS, NS or ISS in their country to continue in the study in an additional extension period II, during which they will receive treatment with somapacitan until somapacitan is available for prescription in their country or October 2027 at the latest. Relevant text regarding the same has been updated. Relevant text regarding extension period II (91 weeks) has also been added.	To ensure that participants finishing extension period I before somapacitan is available for prescription can continue in the trial (in extension period II) and receive treatment.
Section 1.1 Synopsis Section 5.1 Inclusion criteria	A note was included in the ISS inclusion criteria regarding the specific requirements for normal GH secretion values in Korea.	Clarification
Section 1.2 Flowchart for main and extension period I	Column name 'End of treatment' is deleted. Procedures for visits 17, 17A and 18 have been updated.	To accommodate changes due to addition of extension period II

Figure 1 Trial design is updated.

Section # and name	Description of change	Brief rationale
Section 1.3 Flowchart for extension period II	A separate flowchart has been added for the participants entering the extension period II.	To ensure that participants finishing extension period I before somapacitan is available for prescription can continue on treatment.
Section 2.1 Study rationale	Text about clinical study reports and individual DBLs has been modified.	To avoid limitations to DBL and CSR development.
Section 4.3 Justification for dose	Text added to specify the justification for the dose of somapacitan used in extension period II.	Clarification

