Rationale for estimand: The primary estimand assesses the expected safety profile in relation to incidence of AEs for a future population (SGA, TS, NS or ISS) while on somapacitan treatment for 26 weeks, if no treatment discontinuation occurs for any reason.

Secondary estimands

The supportive secondary safety estimand regarding the incidence of AEs possibly or probably related to somapacitan from baseline up to week 26 of somapacitan treatment will be evaluated in a similar way as the primary endpoint including possibly or probably related to somapacitan in the endpoint attribute.

The supportive secondary safety estimand regarding the incidence of AEs from baseline to week 156 of somapacitan treatment will be evaluated in a similar way as the primary endpoint substituting 156 weeks for 26 weeks.

The supportive secondary efficacy estimands will be specified in Section [9.3.3](#).

Overall design:

This is an interventional, multi-national, multi-centre, open-labelled, uncontrolled phase 3 study with a basket design. The study is designed to evaluate safety and efficacy of once-weekly dosing of somapacitan (0.24 mg/kg/week). The main period will consist of 26 weeks of treatment, followed by a 130-week open labelled safety extension period I and a 30-day follow-up period in children with short stature in each of the indications SGA, TS (only females), NS and ISS. Further, participants, who complete the extension period I when somapacitan is not available to be prescribed for children with SGA, TS, NS or ISS in their country, can continue treatment in extension period II which will last until somapacitan becomes available for prescription in their country or October 2027 (at the latest). Participants will receive somapacitan at 0.24 mg/kg/week. A follow-up visit will be conducted 30 days after end of treatment. The study is described in this master protocol and includes four sub-studies – one for each of the above listed indications.

The study consists of:

- an up to 3-week screening period for participants in the indications SGA and ISS
- an up to 6-week screening period for participants in the indications TS and NS
- a 26-week interventional main period
- a 130-week interventional extension period I
- up to 91-week interventional extension period II
- a 30-day follow-up period

For an overview of the study design please see Section [4](#).

Study intervention groups and duration:

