8.3.1 Time period and frequency for collecting AE information

All AEs and SAEs must be collected from the first study-related activity after obtaining informed consent and until the follow-up visit in accordance with the flowchart (Section [1.2](#)) or whenever, within the above time period, the site becomes aware of an AE or SAE.

Information regarding medication errors and injection site reactions must be collected at every visit from baseline until end of treatment.

Conditions present prior to the timepoint from which AEs are collected and anticipated day-to-day fluctuations of these conditions, including those identified during screening or during other study-related procedures performed before exposure to study intervention under clinical investigation, will be recorded as medical history/concomitant illness.

AE and SAE reporting timelines can be found in Appendix 3 (Section [10.3](#)). All SAEs must be recorded and reported to Novo Nordisk without undue delay but not later than within 24 hours of obtaining knowledge of the events. Similarly, the investigator must submit any updated SAE data to Novo Nordisk without undue delay but not later than within 24 hours of obtaining knowledge of the information.

Investigators are not obligated to actively seek for AE or SAE in former study participants. However, if the investigator learns of any SAE with a suspected causal relationship to the IMP or to study participation, occurring after a participant has discontinued/completed the study, the investigator must notify Novo Nordisk without undue delay.

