Change in left ventricle inner dimension end systole (LVIDes) SDS	From baseline (week 0) to visit 7 (week 26).	Score ^b	
Derived as the LVIDes SDS value at baseline week 0 subtracted from LVIDes SDS value at week 26 (visit 7) for Turner syndrome.
 
LVIDes SDS is derived as:
 $\text{LVIDes SDS}_i = \frac{\ln(\text{LVIDes})_i - \text{intercept} + \ln(\text{Weight}_i * \text{slope})}{\text{SD residual}}$ 
where i indicates the visit. The intercept, slope and SD residuals are the ones corresponding to the age at visit i. The intercept, slope and SD residuals are based on reference data.⁵⁸

Title	Time frame	Unit	Details
Change in sitting height/height (SH/H)	From baseline (week 0) to visit 7 (week 26).	Ratio	Derived as SH/H at baseline week 0 subtracted from SH/H at week 26 (visit 7) for TS & ISS .
Change in sitting height/height SDS (SH/H SDS)	From baseline (week 0) to visit 7 (week 26).	Ratio	Derived as SH/H SDS at baseline week 0 subtracted from SH/H SDS at week 26 (visit 7) for TS & ISS . SH/H SDS is derived as: $\text{SH/H SDS}_i = \frac{\left(\frac{\text{SH}/H_i}{\text{population median}} \right)^{\text{Skewness}} - 1}{\text{Skewness} * \text{population SD}}$ where i indicates the visit. The population median and standard deviation are the ones corresponding to the age at visit i.
Change in bone age	From screening (visit 1) to visit 9 (week 52).	Ratio	The bone age/chronological age value at screening (visit 1) subtracted from the bone age value at week 52 (visit 9).

^aNegative score indicates that treatment burden is less compared to baseline.

^bPositive score indicates that the value is closer to or above the reference population compared to baseline.

^cNegative values indicate that the values are lower than the reference population.

^dNegative values indicate that the NAH is below the genetic height potential.

^eOnly to be collected from participants switching to somapacitan from daily GH treatment.

Height Velocity at visit 9 (week 52), Change in Height SDS from baseline (week 0) to visit 9 (week 52), Change in Height Velocity SDS from baseline (week 0) to visit 9 (week 52), Change in IGF-1 SDS from baseline (week 0) to visit 9 (week 52) and Change in IGFBP-3 SDS from baseline (week 0) to visit 9 (week 52) will be derived as parameters in the same way as the corresponding secondary endpoints at visit 7 (week 26).

The parameters will be summarised for relevant indications, SGA, TS, NS or ISS.

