#### 4.2.1 Definition of Endpoint

Number of adverse events (AEs) from baseline (week 0) to week 26.

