##### **4.5.2 Adverse Events**

Adverse events will be displayed as per the primary and secondary endpoints.

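### No planned adverse-event summary runs past week 156, so on-treatment events in extension period II (to week 247 at most) fall outside every AE table, and the on-treatment data set stops at visit 7

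*Protocol*

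**What the plan says.** There are three AE endpoints. The primary, in SAP 4.2.1, is "Number of adverse events (AEs) from baseline (week 0) to week 26". The second, in Protocol 9.3.3, is the "incidence of AEs possibly or probably related to somapacitan from baseline up to week 26 of somapacitan treatment". The third is the long-term one: "incidence of AEs from baseline up to week 156 of somapacitan treatment will be evaluated in a similar way as the primary endpoint", with the longer period substituted. Protocol Table 3-1 and SAP 1.1 give the same windows. On displays, SAP 4.5.2 says: "Adverse events will be displayed as per the primary and secondary endpoints". SAP 4.5.1 (extent of exposure) and 4.5.3 (additional safety assessments) are marked not applicable.

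The current protocol's Synopsis adds an "up to 91-week interventional extension period II", which ends when the product can be prescribed locally or in October 2027. Protocol 8.3.1 states: "All AEs and SAEs must be collected from the first study-related activity after obtaining informed consent and until the follow-up visit". The flowchart in Protocol 1.3 marks AE collection at visits 19 to 25, 98 and 99. The rationale for the amendment says of the added period: "This will allow for collection of additional clinical data on long-term exposure of somapacitan for safety and clinical efficacy".

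Protocol 9.2 and SAP 3 close the On-treatment data points set at the earliest of visit 7, last contact and 14 days after the last dose. They assign that set to the primary estimand and to all other safety data. Protocol 9.3.2 and SAP 4.2, however, count AEs up to the end of treatment or 14 days after the last dose. The SAP is written against protocol 3.0, describes three years of treatment and does not mention extension period II.

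**The concern.** Long-term safety is a secondary objective and part of the case for extension period II. The children who continue will have the longest exposure in the study. If the plan is followed as written, an event type that first appears after week 156 would be recorded but would enter neither the event counts nor the rate per 100 patient-years. The exposure time would be missing from the denominator as well. AEs judged possibly or probably related have no planned summary after week 26.

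The data-set definition adds a second difficulty. The week-156 summary is to be built like the primary one, and the primary one uses a set that cannot extend past visit 7. Someone programming the tables would have to choose between the set definition, the endpoint window and the end-of-treatment sentence. For late safety data in children, that choice should be written down in advance.

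**Working it through.** **1. The plan's own timeline.** Inputs are the period lengths in Protocol 4.1: 26, 130 and up to 91 weeks.
- End of extension I: 26 + 130 = 156 weeks, which matches visit 17.
- End of extension II: 156 + 91 = 247 weeks, which matches visit 25 in Protocol 1.3.

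**2. AE windows against treatment time.**

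| Item | Latest end |
|---|---|
| All AEs (primary) | week 26 |
| Related AEs | week 26 |
| All AEs (long-term) | week 156 |
| On-treatment data set | visit 7 (week 26) |
| Treatment and AE collection | week 247, plus follow-up |

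The gap after the longest AE window is 247 − 156 = 91 weeks, and 91 / 247 = 36.8% of the maximum treatment time per child.

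**3. Does another planned output catch these events?** The only separate AE listing (Protocol 9.3.2, SAP 4.2) holds events starting 14 days or more after the last dose. Events that occur on treatment in extension II do not qualify.

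**4. Was the analysis plan carried forward?** Protocol Table 9-2 now follows near adult height to the end of treatment. SAP 4.6.1 still ends it at visit 18 (week 156). The AE windows were left at week 156 in both documents, so the AE gap is in the current protocol as well as in the older SAP.

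**5. Size of the uncovered exposure.** The number entering extension II is not stated, so it is an assumption here. Patient-years = n × 91 / 52.18, where 52.18 = 365.25 / 7. For comparison, the 40 planned completers followed to week 156 give 40 × 156 / 52.18 = 119.6 patient-years.

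| Children staying the full 91 weeks | Patient-years after week 156 | Share of all exposure |
|---|---|---|
| 10 | 17.4 | 17.4 / 137.0 = 12.7% |
| 20 | 34.9 | 34.9 / 154.5 = 22.6% |
| 40 | 69.8 | 69.8 / 189.4 = 36.8% |

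Summaries are by indication. With ten completers in an indication, exposure to week 156 is 119.6 / 4 = 29.9 patient-years, and extension II could add at most 17.4.

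**The case against.** The strongest reply is that Protocol 9.3.2 and SAP 4.2 already include AEs up to the end of treatment. By footnote j of the flowchart in Protocol 1.2, that point lies in extension II for children who continue. The sentence does not settle the matter. It belongs to the analysis of a 26-week endpoint, on a data set that ends at visit 7, and the long-term version substitutes 156 weeks. What stands is that the texts conflict and need reconciling.

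A fixed common window to week 156 is also defensible. Protocol 4.4 defines completion through extension I and sets no period to be completed in extension II, which serves largely as continued access. That is a good reason to keep the week-156 summary, but it does not argue against adding a cumulative one. SAP 4.5.2 does not contain the word only. That its list is closed is an inference, supported by the absence of any other AE output in the SAP.

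A reader might infer that these events are lost altogether. The documents do not support that. AEs are collected at every extension II visit, and sponsor surveillance and data monitoring committee review (Protocol 10.1.6) carry no stated week-156 limit.

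A reader might also infer that height and IGF-I data after week 52 serve no purpose. That is not so. Later heights feed near adult height, the change in height SDS at that visit and the index of genetic height potential (Protocol 9.3.6). IGF-I data from the study feed the PK/PD modelling. Nor would IGF-I SDS tables at weeks 104 and 208 be a sound addition. Protocol Table 10-4 places those samples 12 to 95 hours after dosing, against 96 to 143 hours at weeks 26, 52 and 156, so sampling time would be mixed with treatment duration.

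**Conclusion.** The point holds for AE summaries. No AE endpoint extends past week 156, AE displays follow the endpoints, and up to 91 weeks of on-treatment events per continuing child are in no planned summary. Separately, the On-treatment set cannot literally support the week-156 summary. The instruction to substitute 156 weeks shows the intent, but the set definition was not changed to match.

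The 17, 35 and 70 patient-years are upper bounds for 10, 20 and 40 continuing children, because each figure assumes the full 91 weeks. Extension II ends early where the product becomes available, and Protocol 7.1 lists reasons for stopping treatment, including reaching near adult height. The 36.8% is likewise a per-child maximum.

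The 26-week primary summary as defined by its endpoint is unaffected, and the study tests no hypotheses. This should be corrected because the plan as written does not fully serve the stated long-term safety objective.

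**What to change.** 1. Update the SAP from protocol 3.0 to the current protocol, including its design description and Section 4.8.
2. In SAP 3 and Protocol 9.2, define an on-treatment set for long-term safety that runs from first dose to 14 days after last dose, without the visit 7 cut. Keep the existing set for the 26-week analyses.
3. Keep the week-26 and week-156 AE summaries. In SAP 4.3.2.1 and 4.5.2, add the same descriptive summary from baseline to end of treatment, including extension II. It should cover all AEs and related AEs, and give number of events and rate per 100 patient-years of actual exposure, by indication.
4. Footnote that numbers after week 156 are few and selected by local product availability.
5. Reconcile the end-of-treatment sentence in Protocol 9.3.2 and SAP 4.2 with the endpoint windows, saying which cut applies to which summary.

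The cost is a SAP revision and further runs of existing descriptive tables, with no new visits or data. If the sponsor also aligns Protocol 9.2, 9.3.3 or Table 3-1, that is a protocol amendment and needs ethics approval under Protocol 10.1.1. It could be bundled with the next planned amendment.
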